### **6.1.3 Ancillary Apparatus**

The final part of the system are ancillary apparatus to aid the nurse in loading the device on a colonoscope.

Document title:	Document No.	Version	Page 17 of 61
Optimizing the Preparation Regime Prior to Colonoscopy Procedure with Pure-Vu System	CL00042	1.0	

- The loading apparatus consists of a pressure source and a distal sealing plug to facilitate inflation of the inner sleeve of the device as well as a base to keep the Oversleeve in a stable position to allow insertion of the colonoscope through the inner sleeve.

## 6.2 Pre-clinical data

The Pure-Vu system was used by four experienced gastroenterologists in 35 Yorkshire cross swine (66% female) that received a reduced bowel preparation to ensure an inadequate bowel preparation at baseline. Prior to the colonoscopy the Pure-Vu was attached to the colonoscope and the baseline prep was assessed during insertion. The Pure-Vu system was then employed to cleanse the colon and the prep was then assessed post-Pure-Vu use.

No adverse effects and no failed or prematurely terminated cases were noted. Fourteen percent of the swine colons were adequately prepped at baseline (mean BBPS score  $0.5 \pm 0.7$ ) and improved to 100% after use of Pure-Vu ( $p < 0.001$ ) (mean BBPS score  $3.0 \pm 0.0$ ). The physicians found Pure-Vu easy and intuitive to operate.

The Pure-Vu system effectively cleaned inadequately prepped swine colons and proved to be easy to use.

## 6.3 Clinical data to Date

The latest Pure-Vu System tested in ninety-seven subjects (54% males) from five sites using similar protocol.

Pure-Vu was used in subjects with a partially prepped receiving a colonoscopy for screening, diagnostic or surveillance.

To ensure an inadequately prepped colon subjects underwent a reduced preparation consisting of dietary restrictions (no dried fruit, seeds or nuts) starting 2 days prior to the colonoscopy, an 18 to 24 hour clear liquid diet and a split dose of 20mg Bisacodyl.

The cleansing quality was evaluated before and after use of the Pure-Vu System with the Boston Bowel Preparation Score (BBPS) (1).

Two patients were excluded from the analysis due to the followings:

Document title:	Document No.	Version	Page 18 of 61
Optimizing the Preparation Regime Prior to Colonoscopy Procedure with Pure-Vu System	CL00042	1.0	

- One patient who had breakfast on day of procedure was excluded from the cleansing efficacy and usability analysis due to non-compliance with the pre-procedural prep regimen.
- In one patients the device could not reach beyond the sigmoid colon due to the patient's anatomy, thus the physician used a slim colonoscope to complete the procedure and indicated that only a slim colonoscope would be able to advance past the sigmoid and into the cecum.

The Pure-Vu significantly increased the number of subjects with an adequate cleansing level (BBPS  $\geq 2$  for all 3 colon segments) from 25%; CI 95% [17%, 35%] at baseline to 99%; CI 95% [94%, 100%] after Pure-Vu. Cecum intubation rate was 98%; CI 95% [94%, 100%]). Mean post-treatment BBPS score was  $8.7 \pm 1.0$  vs.  $3.9 \pm 2.2$  prior to Pure-Vu use. Physicians were satisfied with the device's use. No major difficulties were experienced when performing polypectomy and no serious adverse events were reported.

## 7.0 Risk/Benefit Analysis

### 7.1 Anticipated Risks Associated with Pure-Vu System conjunction with a standard colonoscope

The Pure-Vu is used in conjunction with a standard colonoscope during a colonoscopy procedure. Hence, the complications associated with using the Pure-Vu are anticipated to be similar to those associated with the colonoscopy procedure. As with any colonoscopy procedure, when using the Pure-Vu there is some risk of bowel perforation, pain, infection and bleeding. Although the risks of the procedure with the Pure-Vu System are expected to be comparable to conventional colonoscope (0.35%), the device is an Oversleeve to a standard colonoscope. Hence, diameter is bigger, and the cleansing time may add some minutes to the procedure time. a potential risks associated with the participation in the clinical investigation may include a repeated colonoscopy procedure as the subjects enrolled to the study are required to undergo a limited prep as compared to the preparation given prior to standard colonoscopy procedure.

The latest Pure-Vu version was tested in an animal study including 35 pigs and in preliminary clinical studies including 97 subjects.

Document title:	Document No.	Version	Page 19 of 61
Optimizing the Preparation Regime Prior to Colonoscopy Procedure with Pure-Vu System	CL00042	1.0	

No major complication or serious adverse events occurred within the course of those studies.

In addition, these clinical studies demonstrated an excellent cleansing effectiveness; Pure-Vu improved the cleansing level from 25% at baseline to 99% after the cleansing was operated and in 98% of the patients the cecum was reached and the procedures completed successfully. Efficacy results support the study design rationale that decreases the risks associated with the preparation without increasing the risk related to incomplete/ repeated colonoscopy procedure.

Lastly, patients to be enrolled to this study shall be eligible to colonoscopy, thus the risks detailed above covers all the population intended to participate in the study.

Considering the residual risks and the potential and the risk against benefit assessment, it can be concluded that the system may offer potential benefit to the patients along with no significant risk increase.

## 7.2 Anticipated Risks Associated with bowel preparation agents

The Bowel preparation agent used in this study are approved in U.S.

The main anticipated risks associated with the bowel preparation agents including nausea with or without vomiting, abdominal pain and dehydration.

The preparation in this study is less intensive compared to the standard preparation done prior to colonoscopy procedure, thus we expect that the risks related to the preparation agent will be similar or even lower than the risks following a standard preparation to colonoscopy procedure.

Reduction of the bowel preparation regimen will minimize patient discomfort and AEs associated with bowel cleansing, and potentially maximize the efficacy of the colonoscopy procedure with Pure-Vu System.

## 7.3 Residual risk associated with the investigational device

The residual risk is the risk remaining after the risk controls have been implemented.

The residual risk is evaluated according to the following:

- Acceptable Residual risk includes all RPN  $\leq 9$ .
- Risks rated 10-16 will be acceptable if the risk benefit ratio justifies it.

All risks of using Pure-Vu were mitigated by risk management process according to EN ISO 14971:2012.

Document title:	Document No.	Version	Page 20 of 61
Optimizing the Preparation Regime Prior to Colonoscopy Procedure with Pure-Vu System	CL00042	1.0	

The mitigation to the risks associated with the investigational device includes but is not limited to the followings:

- Smooth head shape that contains lumens for cleansing jets and evacuation. The lumens' size were optimized to ensure the safety of the patients along with effective cleansing.
- The Pure-Vu Oversleeve are made from a flexible and low friction material to allow ease advancement through the colon and to minimize any impact to the steering angle of the colonoscope.
- Hydrophilic coating at the distal 30cm of the outer sleeve to create a lubricious surface to allow ease insertion and advancement.
- Cleansing procedure can be operated in 3 modes (low, medium, high), where the physician can control the intensity of cleansing jets to ensure the safety of the patients along with effective cleansing.

The potential residual risk following the mitigations are all acceptable (for more details please refer to "Risk analysis report").

#### 7.4 Potential Benefits to the Subject

The potential benefits of the Pure-Vu System are utilization of a cleaning technology that may improve the standard colonoscopy visualization, reduce reliance on subject pre-procedure colon preparation for ensuring high quality colonoscopy, increase the subject compliance to colonoscopy procedure and reduce the need for repeated colonoscopies required due to insufficient colon preparation, these consequently may reduce pain, discomfort, risk and cost.

The reduce bowel preparation required when Pure- Vu System is used as compare to standard preparation required prior to colonoscopy procedure without the Pure-Vu System, may increase the subject compliance to the colonoscopy procedure and may reduce the patient's discomfort caused by the preparation regimens.

Considering the residual risks and the risk against benefit assessment, it can be concluded that the system may offer potential benefit to the patients along with no significant risk increase compared to the standard of care procedure.

Document title:	Document No.	Version	Page 21 of 61
Optimizing the Preparation Regime Prior to Colonoscopy Procedure with Pure-Vu System	CL00042	1.0	

## 8.0 Study Objectives

### 8.1 Primary objective

To evaluate the performance of Pure-Vu System in cleansing patients' colon who are indicated for a colonoscopy procedure using one of two different bowel preparation regimes.

### 8.2 Secondary objectives:

- To evaluate the safety related to the Pure-Vu System in both study arms.
- To evaluate the time to reach the Cecum in Pure-Vu procedures in both study arms.
- To evaluate the total procedure time with Pure-Vu in both study arms.
- To evaluate the cecal intubation rate with Pure-Vu in both study arms.
- To evaluate patients' satisfaction with Pure-Vu procedure in both study arms.
- To evaluate Pure-Vu user satisfaction with Pure-Vu procedure in both study arms.

## 9.0 Study Design

This multicenter, prospective, randomized study will include up to 100 patients (30 patients per site and 15 patients per study arm), aimed at evaluating the performance of Pure-Vu System in cleansing patients' colon who are indicated for colonoscopy procedure using one of two different preparation regimes as detailed below.

[figure not shown]
Subjects will be enrolled at up to 10 clinical sites in the United States. Subjects who meet the eligibility criteria will be randomly allocated to a given study arm and will be required to follow a specific bowel preparation instruction along with a specific prep agent (Bowel preparation instructions for morning and afternoon procedures are provided in appendix B1 and B2, respectively), as per study arm allocation, starting 5 days prior to the colonoscopy with Pure-Vu. Patients will be asked to record and provide their diet and bowel movements in the provided diary log at time of their scheduled colonoscopy (Diary log is provided in appendix D).

In addition patient will be asked to complete a satisfaction questionnaire include feedback on the procedure and on specific aspects related to the preparation regime.

Following the procedure a telephone follow-up will be conducted at 48 hours ( $\pm$  48 hours) post Pure-Vu procedure to assess patient well-being and capture any adverse events.

Document title:	Document No.	Version	Page 22 of 61
Optimizing the Preparation Regime Prior to Colonoscopy Procedure with Pure-Vu System	CL00042	1.0	

### Study Flow chart

#### 9.1 Primary Endpoint

The primary endpoint is the rate of adequate cleansing level per subject evaluated by the BBPS scoring index pre- and post the cleansing operation.

#### 9.2 Secondary Endpoints

The following secondary outcomes will be determined:

- AEs

Document title:	Document No.	Version	Page 23 of 61
Optimizing the Preparation Regime Prior to Colonoscopy Procedure with Pure-Vu System	CL00042	1.0	

- Rate of procedures where the cecum was visualized.
- Time to reach the cecum.
- Total procedure time.
- User satisfaction will be evaluated by a questionnaire filled-in by the physicians and nurses who conduct the procedures and assemble the Pure-Vu System.

## 10.0 Subject Selection and Enrollment

After being informed of the nature of the study, the subject will sign a written informed consent form (ICF) that has been approved by the appropriate IRB of the respective clinical site. Enrollment of up to 100 subjects is planned.

Subjects' participation in the study will last approximately 8 days, including the procedure day, five days prior for bowel preparation, and the follow up period.

Subjects will be considered for the study if they meet the specific inclusion/exclusion criteria. The criteria for enrollment must be followed explicitly.

Enrollment completion is expected to take place up to 12 months following IRB approval of the study.

### 10.1 Inclusion Criteria

1. Subjects scheduled for colonoscopy procedure
2. Subjects in the age range of 22-75 years inclusive
3. Subject is willing and able to participate in the study procedures and to understand and sign the informed consent.

### 10.2 Exclusion Criteria

1. Patients with active Inflammatory Bowel Disease
2. Patients with known diverticulitis disease or with prior incomplete colonoscopy due to diverticular disease

Document title:	Document No.	Version	Page 24 of 61
Optimizing the Preparation Regime Prior to Colonoscopy Procedure with Pure-Vu System	CL00042	1.0	

3. Patients with known bowel obstruction
4. Patient with chronic constipation
5. History of prior surgery to colon and/or rectum
6. ASA  $\geq$  III
7. Renal insufficiency (Creatinine  $\geq$  1.5mg /dL) (based on medical history)
8. Abnormal Liver enzymes (ALT/AST  $\geq$  2 times upper limits of normal) (based on medical history)
9. Patients taking anticoagulants drugs (excluding aspirin) or dual antiplatelet therapy
10. Patients with known coagulation disorder (INR  $>$ 1.5).
11. Pregnancy (as stated by patient) or breast feeding
12. Patients with altered mental status/inability to provide informed consent

### 10.3 Withdrawal Criteria

Subjects may withdraw from the study at their own request or at the request of their legally acceptable representative. The investigator may withdraw a subject from the study at any time for the following reasons:

- Severe side effects clearly related to the study device.
- Presence or appearance of exclusion criteria.
- Appearance of accompanying diseases rendering further participation in the study impossible.
- A significant protocol violation, as determined either by the sponsor or the investigator
- Subject noncompliant with investigational procedures
- Subject noncompliant with visits
- At the specific reasonable request of the sponsor

The sponsor must be informed in each withdrawal case. The reason for withdrawal must be recorded in the CRF and in the patient file.

Document title:	Document No.	Version	Page 25 of 61
Optimizing the Preparation Regime Prior to Colonoscopy Procedure with Pure-Vu System	CL00042	1.0	

## 10.4 Selection of Investigators and Training

Board-certified gastroenterologists in accordance with US and hospital guidelines will be considered for participation as investigators in this study. Physicians in training (residents, fellows) and physician assistants may assist the Study Investigator in any aspect of the procedure as per standard procedures and practices at his/her institution.

Each Investigator participating in the clinical trial and the associated clinical study staff will receive training on the clinical protocol. This includes training on AE reporting, case report form (CRF) completion, and Good Clinical Practice (GCP), as well as the device and system (including procedural use, device characteristics, shelf life and storage requirements, warnings, and precautions).

## 11.0 Study Procedures

### 11.1.1 Screening and Informed Consent (Visit 1)

Subjects participating in the study may be recruited from investigator's patients' pool.

A screening/baseline visit will be performed within 30 days prior to the scheduled Pure-Vu procedure to assess preoperative eligibility. In the event that the screening and eligibility assessment takes place more than 30 days prior to the planned procedure date, the investigator should contact the subject prior to the procedure date to assure there is no change in the subject's medical condition.

At the screening visit, subjects will be approached to obtain written informed consent prior to any study specific procedures being performed. The purpose of the study and the benefits and risks of the procedures will be explained to the subject and the consent process must be documented accordingly in the medical record. Subjects who agree to study participation must sign an IRB-approved ICF. Subjects will be informed that their participation in this study is voluntary and they may refuse to participate or discontinue from the study at any time. Subjects will be given the opportunity to ask the investigator questions so that they are adequately informed about the research. A copy of the signed informed consent must be provided to the subject and the informed consent process will be documented in source documents.

If new information becomes available that may affect a subject's decision to continue to take part in the study, this information will be discussed with the subject by the investigator.

Document title:	Document No.	Version	Page 26 of 61
Optimizing the Preparation Regime Prior to Colonoscopy Procedure with Pure-Vu System	CL00042	1.0	

The following assessments will be performed within 30 days prior to the scheduled procedure and the results recorded on the appropriate subject CRFs:

- Verification of eligibility criteria and subject risk per guidelines
- Demographics (age, gender, height, weight)
- Surgical and medical history (prior abdominal surgery, GI symptoms)
- General medical history will be assessed based on the subject's clinical condition

#### **Recruitment visit:**

Patients who meet the eligibility criteria will be screened for study participation and will be randomly allocated to a given study arm at a baseline visit. Patients who are eligible for the study will be required to follow a specific bowel preparation instruction along with a specific prep agent, (Detailed instructions of the study Bowel preparations are provided in appendix B1 and B2) as per study arm allocation, starting 5 days prior to the colonoscopy with Pure-Vu. Subject diaries are provided to the subject at visit 1 to be and will be filled by the subjects during the preparation phase. This will include diet and bowel movement information (diary log is provided in appendix D). The subject is instructed to bring the diary with him/her to the scheduled colonoscopy.

In addition patient satisfaction questionnaire will be provide include feedback on the procedure and on specific aspects related to the preparation regime.

#### **11.1.2 Randomization**

Randomization in blocks will be applied for each site to allocate patients to one of two different bowel preparation regimens (Prep A versus Prep B). The study will utilize randomization in blocks using the standard envelope procedure, which will be applied in order to allocate patients into two arms:

- Group 1 - Will go through the Prep A procedure
- Group 2 - Will go through the Prep B procedure

The site randomization plan will be provided to the study coordinator prior the study start. No blinding is applicable in this study.

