#### **11.1.4 Colon Preparation**

Subjects will be instructed to follow a detailed dietary and colon preparation regimen prior to the procedure day. All colon preparation products will be standard colon cleansing products approved by the FDA.

Patients will be randomized to one of two bowel preparation regimens (instruction for bowel preparation for morning and afternoon procedures are provided in appendix B1 and B2).

Subjects will keep a timed diary of key preparation steps and bowel activity, in addition questions about the patients satisfaction from the bowel preparation regime and diet instruction will be captured (Appendix D).

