### Time analysis

T-tests for continuous variables will be performed in order to evaluate the difference between the two preparation procedures for the following endpoints:

- Time to Cecum- defined as the duration from colonoscope insertion to visualization of the cecum.

Document title:	Document No.	Version	Page 31 of 61
Optimizing the Preparation Regime Prior to Colonoscopy Procedure with Pure-Vu System	CL00042	1.0	

- Total Procedure time- defined as the time from colonoscope insertion to removal. (guide: >6 minutes withdrawal time)

These endpoints will be summarized using descriptive statistics, including number of subjects, mean, median, standard deviation, minimum, and maximum.

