***Drink at least two liters of CLEAR LIQUIDS per day beginning at 2 days prior to your procedure***

On the day before your Procedure You Can Eat the Following:

Breakfast	 20 oz of clear liquid  1-2 slices of white bread + cheese spread/ cottage cheese/ butter/ margarine/ 1 Tablespoon of mayonnaise/ honey  1 plain yogurt/sour cream  Scrambled eggs ( 1-2 eggs)  Tea sweetened with white sugar or coffee added with a small amount of milk
Lunch	 20 oz of clear liquid  1-2 slices of white bread with cheese spread, butter, margarine, honey.  4-6 oz of chicken soup containing skinless chicken and peeled potato.  Pasta or noodles with butter (no red sauce) or white rice
Dinner	 20 oz of clear liquid  1-2 slices of white bread + cheese spread/ cottage cheese/ butter/ margarine/ 1 Tablespoon of mayonnaise/ honey  1 plain yogurt/sour cream  Pasta or noodles with butter (no red sauce) or white rice  Clear chicken soup  Tea sweetened with white sugar or coffee added with a small amount of milk

On the day of your Procedure You Can Eat a light breakfast as the Following:

Breakfast	 20 oz of clear liquid  1-2 slices of white bread + cheese spread/ cottage cheese/ butter/ margarine/ 1 Tablespoon of mayonnaise/ honey  1 plain yogurt/sour cream  Tea sweetened with white sugar or coffee without milk/cream
------------------	--

Clear-liquid diet up to 3 hours prior to the procedure

Fasting (no food / liquids) start 3 hours prior to procedure time

Document title:  Optimizing the Preparation Regime Prior to Colonoscopy Procedure with Pure-Vu System	Document No.  CL00042	Version  1.0	Page 50 of 61
---	------------------------------------	---------------------------	------------------

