## 24.0 Appendix F – Case Report Form (filled-in by the physician)

**Site No.      Subject No.      Subject Initials**

Study arm:  Magnesium Citrate 10 oz  Magnesium Citrate 15 oz

**Physician Name:** \_\_\_\_\_

Date subject signed the informed consent form: \_\_\_\_ / \_\_\_\_ / \_\_\_\_  
DD MM YY

Date investigator/designee signed the informed consent form: \_\_\_\_ / \_\_\_\_ / \_\_\_\_  
DD MM YY

Did the subject satisfy all enrollment criteria?  Yes  No (if No, please specify which criterion was not met)

**Patient Gender / Age:** \_\_\_\_\_ / \_\_\_\_\_

**Patient Height (cm) / Weight (kg):** \_\_\_\_\_ / \_\_\_\_\_

Please check all indications that apply for the patients' colonoscopy	Please Check
Screening	
Bleeding	
Polyp surveillance	

CONFIDENTIAL

Document title:  Optimizing the Preparation Regime Prior to Colonoscopy Procedure with Pure-Vu System	Document No.  CL00042	Version  1.0	Page 57 of 61
---	------------------------------------	---------------------------	---------------

IBD surveillance	
Family history (1st degree relative)	
Anemia	
Other: Please specify	

Prescribed Prep	Completed Yes / No
Magnesium Citrate 10oz:	
Magnesium Citrate 15oz:	

	HH : MM
Colonoscopy start time	
Time cecum reached	
Time colonoscopy ended	

Please rate the bowel prep	BBPS Rating Prior to Use of Pure-Vu (0 - 3)	BBPS Rating After Use of Pure-Vu (0 - 3)
Descending colon		
Transverse colon		
Ascending colon		

Comments: \_\_\_\_\_

Document title:  Optimizing the Preparation Regime Prior to Colonoscopy Procedure with Pure-Vu System	Document No.  CL00042	Version  1.0	Page 58 of 61
---	------------------------------------	---------------------------	------------------

	Sigmoid / Descending	Transverse	Ascending
If the cecum was not reached during the colonoscopy procedure, please indicate the furthest anatomical landmark reached			

If cecum not reached, please indicate the reason	Please Check
Poor bowel cleanliness	
Patient intolerance / discomfort	
Clinical and anatomical (such as stricture, redundant colon, etc.)	
Other: Please specify	
_____	
_____	
_____	

Usability	Excellent	Good	Acceptable	Difficult	Unacceptable
Ease of colonoscope advancement with Pure-Vu					
Ease of navigating colonoscope with Pure-Vu					
Torque ability of colonoscope with Pure-Vu					
Ease of sigmoid passing					
Ease of retroflex					

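### Slot (morning or afternoon) changes the procedure-day diet, but is neither fixed before allocation nor used in the comparisons: a minor gap costing precision and leaving arm-dependent booking possible

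*Protocol*

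**What the plan says.** On allocation, section 11.1.2 states "Randomization in blocks will be applied for each site to allocate patients to one of two different bowel preparation regimens". Envelopes are used, "The site randomization plan will be provided to the study coordinator prior the study start", and "No blinding is applicable in this study".

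On slots, section 9.0 states "Bowel preparation instructions for morning and afternoon procedures are provided in appendix B1 and B2, respectively", and section 11.1.4 repeats this. The two charts are figures that are not shown. The diet sheets in Appendix D are readable. The morning sheet (22.1) gives only clear liquids and then fasting on the procedure day. The afternoon sheet (22.2) adds solid food: "On the day of your Procedure You Can Eat a light breakfast as the Following", with bread, spread and yogurt on the list. The synopsis gives the clear-liquid rule alone, with no split by slot.

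On analysis, sections 12.3 and 12.4 compare arms by chi-square or Fisher's exact test for cleansing, cecal intubation and satisfaction. For time to cecum and total procedure time: "T-tests for continuous variables will be performed in order to evaluate the difference between the two preparation procedures". No site or slot term appears. The physician CRF (Appendix F) has a clock field, "Colonoscopy start time", but no field for the booked slot.

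**The concern.** The trial compares two preparations, and slot alters part of the preparation within each arm. If slot affects cleansing, procedure time or tolerability, uneven slot mixes shift the arm comparison, and even an equal mix adds variance that an unadjusted test leaves in.

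The sponsor's own history makes a slot effect plausible. In the earlier study (section 6.3), one patient who ate breakfast on the procedure day was left out of the cleansing analysis. The reason given was non-compliance with that study's regimen, so this shows that the food rule was taken seriously; it does not measure an effect.

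The conduct side matters separately. Allocation is open and made at the baseline visit, which may be 30 days or more before the procedure. Nothing stops a slot being chosen or changed once the arm is known, and the CRF would not reveal it, because only the actual start time is kept.

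**Working it through.** The protocol gives no power, effect size, afternoon share or slot effect, so there is no stated figure to reproduce. The calculations below are illustrations.

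**Inputs.** 45 per arm follows from 15 per arm per site (section 9.0) at 3 sites (synopsis). 50 per arm follows from up to 100 patients. Earlier adequacy was 25% before and 99% after cleansing (section 6.3). Assumed: afternoon share 30% to 50%, two-sided 5% level, and the slot effects stated below.

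**1. Was the slot known at allocation?** Section 10.1 admits patients who already have a colonoscopy scheduled. Section 11.1.1 times screening against that date. Appendix A puts randomisation, preparation instructions and diaries all at Visit 1, and those materials are slot-specific. This points to a slot known by the end of Visit 1. The order within the visit, and later rebooking, are left open.

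**2. Chance imbalance if the slot is fixed first.** The gap in afternoon share has mean 0 and SD = 2·√(q(1−q)/(2n−1)), with n per arm and q the afternoon share.

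| n per arm | q | SD of gap | P(gap ≥ 10 points) | P(gap ≥ 20 points) |
|---|---|---|---|---|
| 45 | 0.3 | 0.097 | 0.358 | 0.065 |
| 45 | 0.5 | 0.106 | 0.399 | 0.091 |
| 50 | 0.3 | 0.092 | 0.275 | 0.049 |
| 50 | 0.5 | 0.101 | 0.317 | 0.071 |

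**3. Shift in the arm difference = gap × slot effect.**
- Post-cleansing adequacy, assumed slot effect 5 to 10 points, gap 10 to 20 points: 0.10 × 5 = 0.5 to 0.20 × 10 = 2 points.
- Pre-cleansing adequacy, assumed slot effect 20 points, gap 20 points: 0.20 × 20 = 4 points. The standard error at 25% is √(2 × 0.25 × 0.75/n) = 9.1 points (n = 45) or 8.7 (n = 50), so this is under half a standard error.

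**4. Precision for the time outcomes.** With a half-and-half slot split and a shift of d within-slot SDs, slot explains 0.25d²/(1 + 0.25d²) of the variance. For d = 0.5 this is 0.0625/1.0625 = 5.9%; for d = 1 it is 0.25/1.25 = 20%. The standard error falls by 1 − √0.941 = 3% and 1 − √0.80 = 11%. Both values of d are assumptions.

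**5. If booking did depend on the arm.** Assume 30% afternoon in one arm and 70% in the other, no preparation effect, and Fisher's test at 50 per arm. The last two columns give rejection probabilities.

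| Assumed adequacy, morning / afternoon | False difference | Equal slot mix | 30% v 70% |
|---|---|---|---|
| 99% / 94% | 2 points | 0.003 | 0.008 |
| 99% / 89% | 4 points | 0.010 | 0.041 |
| 95% / 75% | 8 points | 0.024 | 0.127 |

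At this mix, only the last row exceeds 5%, and its rates are well below the 99% seen before. A more extreme mix of 10% v 90% with 99% / 89% gives 8 points and 0.190.

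**The case against.** The strongest reply is that a slot set before randomisation is an ordinary baseline covariate. Randomisation balances it in expectation, the planned tests already allow for chance imbalance in their error rates, and using slot-specific instructions in both arms is no flaw. Covariate adjustment could also sit in a statistical analysis plan that is not shown. All of this stands, and so the missing slot term is not an error in the tests.

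A reader might infer that staff choose the slot after seeing the arm and that slot therefore confounds the comparison. The documents do not say so, and the scheduling passages lean the other way; what exists is a silence. A reader might also infer that the dosing interval differs between slots. That cannot be checked, because the two charts are not shown; only the diet difference is verifiable.

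A stratified test of post-cleansing adequacy would gain little. Site by slot gives 6 strata at 3 sites, or 20 at the 10 sites named in section 9.0. At 99% adequacy about 0.5 failures are expected among 50 patients, so most strata would be uninformative.

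Two things survive. The order of booking and envelope opening is trial conduct, which no analysis plan can restore afterwards. And the protocol itself names t-tests that omit even the site factor used in randomisation, where a model with site and slot costs almost nothing.

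**Conclusion.** The point holds in limited form and is minor for a pilot declared unpowered (sections 12.1 and 12.7). Procedure-day diet differs by slot, slot is in neither the randomisation nor the stated comparisons, and nothing fixes it before allocation. If the procedure is scheduled beforehand, as the text suggests, expected bias is zero. What remains is a slot-share gap with an SD of about 10 points and, for the times, perhaps 6% to 20% of variance left unremoved, if slots differ by 0.5 to 1 SD. Systematic bias would require arm-dependent booking, for which the documents give an opening but no evidence. The effect on post-cleansing adequacy is probably small; pre-cleansing BBPS, times and tolerability have more room to move. Every slot effect size here is an assumption.

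**What to change.** - **Section 11.1.2:** state that the slot (morning or afternoon) is booked and recorded before the envelope is opened, and that any later change is recorded with its reason. This protects only if whoever books cannot see the next assignment, so the sentence on giving the site plan to the coordinator should be read with that in mind.
- **Section 12.4:** replace the t-tests for time to cecum and total procedure time with a linear model containing arm, site and booked slot. Booked slot is preferable to slot derived from the start time, which could itself reflect rebooking after allocation.
- **Cleansing outcomes:** show adequacy before and after cleansing by slot within arm, descriptively. Do not add a stratified test of post-cleansing adequacy when failures are few.
- **Procedure-day diet:** reconcile the synopsis with Appendix D 22.1 and 22.2. Which rule applies is for the clinical team.

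The cost is one CRF tick-box, one or two sentences in 11.1.2, two added model terms and one table. Sample size and arms do not change.
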